10.6 Appendix 6: Abbreviations

| Abbreviation | Definition |
|----------------------------|---|
| AE | Adverse event |
| Ae,f | Amount excreted in feces |
| AESI | Adverse event of special interest |
| Ae,u | Amount excreted in urine |
| ALARA | as low as (is) reasonably achievable |
| ALT | Alanine aminotransferase |
| API | Active pharmaceutical ingredient |
| AST | Aspartate aminotransferase |
| AUC | Area under the concentration-time curve |
| AUC _∞ | Area under the concentration-time curve from time zero to infinity |
| AUC _t | Area under the concentration-time curve calculated to the last observable concentration at time t |
| CL | Total body clearance |
| C _{max} | Maximum peak concentration of the drug |
| CRU | Clinical Research Unit |
| EC | Ethics Committee |
| ECG | Electrocardiogram |
| eCRF | Electronic case report form |
| EDC | Electronic data capture |
| %fe,f | Percentage excreted in feces |
| %fe,u | Percentage excreted in urine |
| GCP | Good Clinical Practice |
| HGB | Hemoglobin |
| HIV | Human immunodeficiency virus |
| IB | Investigator's Brochure |
| ICF | Informed consent form |
| ICH | International Council for Harmonisation |
| ICRP | International Commission in Radiological Protection |
| IMP | Investigational medicinal product |
| IRE | Immediately reportable event |
| IV | Intravenous |
| PHE | Public Health England |
| PK | Pharmacokinetic |
| PQC | Product quality complaint |
| SAE | Serious adverse event |
| t _{1/2} | Elimination half-life |
| t _{1/2,z} | Terminal-phase elimination half-life |
| TEAE | Treatment-emergent adverse event |
| t _{max} | Time to reach maximum peak concentration |
| ULN | Upper limit of normal |

10.7 Appendix 7: Protocol Amendments

The investigator will not make any changes to this protocol without the sponsor's prior written consent and subsequent approval/favorable opinion by the EC. Any permanent change to the protocol, whether an overall change or a change for specific trial site, must be handled as a protocol amendment. Any amendment will be written by the sponsor.

Each amendment will be submitted to the EC, as required by local regulations. Except for "administrative" or "nonsubstantial" amendments, investigators will wait for EC approval/favorable opinion of the amended protocol before implementing the change(s). Administrative amendments are defined as having no effect on the safety of subjects, conduct or management of the trial, trial design, or the quality or safety of IMP used in the trial. A protocol change intended to eliminate an apparent immediate hazard to subjects should be implemented immediately after agreement by the sponsor and investigator, followed by EC notification within local applicable timelines. The sponsor will submit protocol amendments to the applicable regulatory agencies within local applicable timelines.

When the EC, investigators, and/or the sponsor conclude that the protocol amendment substantially alters the trial design and/or increases the potential risk to the subject, the currently approved written ICF will require similar modification. In such cases, after approval/favorable opinion of the new ICF by the EC, repeat written informed consent will be obtained from subjects enrolled in the trial before expecting continued participation and before the amendment-specified changes in the trial are implemented.

AUC	area under the concentration-time curve
AUC _∞	area under the concentration-time curve from time 0 to infinity
AUC _t	area under the concentration-time curve calculated to the last observable concentration at time t
BLQ	below the limit of quantification
CDISC	Clinical Data Interchange Standards Consortium
CL	total body clearance
C _{max}	maximum peak concentration
CSR	clinical study report
CV%	coefficient of variation
ECG	electrocardiogram
ICF	informed consent form
ICH	International Council for/Conference on Harmonisation of Technical Requirements for Registration of Pharmaceuticals for Human Use
IV	intravenous
LLOQ	lower limit of quantification
MedDRA	Medical Dictionary for Regulatory Activities
NC	not calculated
NR	no result
NS	no sample
PK	pharmacokinetic(s)
PT	preferred term
R ² -adj	adjusted coefficient for determination of exponential fit
SAP	statistical analysis plan
SD	standard deviation
t _{1/2,z}	terminal-phase elimination half-life
TEAE	treatment-emergent adverse event
TFL	table, figure, and listing
t _{last}	time of last measurable (positive) concentration
t _{max}	time to maximum peak concentration
WHODrug	World Health Organization Drug Dictionary
λ _z	apparent terminal elimination rate constant
λ _z Lower	start of exponential fit
λ _z N	number of data points included in the log-linear regression

λ_z Span Ratio	time period over which λ_z was determined as a ratio of $t_{1/2,z}$
λ_z Upper	end of exponential fit
%AUC _{extrap}	percentage of AUC that is due to extrapolation from the last measurable concentration to infinity

1. INTRODUCTION

This SAP has been developed after review of the clinical study protocol (Final Version 1.0 dated 17 June 2019 and Amendment 1.0 dated 14 November 2019) and electronic case report form.

This SAP describes the planned analysis of the pharmacokinetic (PK), safety and tolerability data from this study. A detailed description of the planned TFLs to be presented in the clinical study report (CSR) is provided in the accompanying TFL shells document.

In general, the analyses are based on information from the protocol, unless they have been modified by agreement with Otsuka Pharmaceutical Co., Ltd. A limited amount of information about this study (eg, objectives, study design) is given to help the reader's interpretation. This SAP must be finalized prior to the lock of the clinical database for this study. When the SAP and TFL shells are approved, they will serve as the template for this study's CSR.

This SAP supersedes any statistical considerations identified in the protocol; where considerations are substantially different, they will be so identified. If additional analyses are required to supplement the planned analyses described in this SAP, they may be performed and will be identified accordingly in the CSR. Any substantial deviations from this SAP will be agreed with Otsuka Pharmaceutical Co., Ltd and identified in the CSR.

This SAP is written with consideration of the recommendations outlined in the International Conference on Harmonisation (ICH) E9 guideline *Statistical Principles for Clinical Trials* and ICH E3 guideline *Structure and Content of Clinical Study Reports*.^{1,2}

The document history is presented in [Appendix 1](#).

2. STUDY OBJECTIVES

2.1. Primary Objectives

- To determine the mass balance of total radioactivity following a single intravenous (IV) infusion of (¹⁴C)-OPC-61815.
- To determine routes and rates of elimination of total radioactivity following a single IV infusion of (¹⁴C)-OPC-61815.
- To assess the PK of total radioactivity in plasma and whole blood following a single IV infusion of (¹⁴C)-OPC-61815.
- To assess the PK of OPC-61815 free form and OPC-41061 in plasma following a single IV infusion of (¹⁴C)-OPC-61815.
- To identify and characterize metabolites in plasma, urine, and feces following a single IV infusion of (¹⁴C)-OPC-61815.

2.2. Secondary Objective

- To assess the safety and tolerability of a single IV infusion of (¹⁴C)-OPC-61815.

3. STUDY ENDPOINTS

3.1. Primary Endpoints

The PK parameter endpoints for OPC-61815 free form and OPC-41061 in plasma, and total radioactivity in whole blood and plasma are:

- Area under the concentration-time curve (AUC) from time 0 to infinity (AUC_∞)
- AUC calculated to the last observable concentration at time t (AUC_t)
- maximum peak concentration (C_{max}),
- time to maximum peak concentration (t_{max})
- time of last measurable (positive) concentration (t_{last})
- terminal-phase elimination half-life (t_{1/2,z})

The total body clearance (CL) will also be determined for OPC-61815 free form. In addition, AUC ratios of whole blood total radioactivity relative to plasma total radioactivity (ratios of Blood/Plasma Ratio for both AUC_∞ and AUC_t) will be calculated.

The following PK parameter endpoints for total radioactivity in urine (calculated and reported separately in the radioanalysis report “Analysis of Total Radioactivity in Blood, Plasma and Excreta” [Covance study: 8405603] by Covance Laboratories) are:

- amount excreted in urine per sampling interval (Ae_u)
- cumulative Ae_u,
- percentage of drug dose excreted in urine per sampling interval (%fe_u)
- cumulative %fe_u

The following PK parameter endpoints for total radioactivity in feces (calculated and reported separately in the radioanalysis report by Covance Laboratories) are:

- amount excreted in feces per sampling interval (Ae_f)
- cumulative Ae_f,
- percentage of drug dose excreted in feces per sampling interval (%fe_f)
- cumulative %fe_f

Overall amount and percent of total radioactivity in excreta (combined urine and feces per sampling interval and cumulative; calculated and reported separately in the radioanalysis report by Covance Laboratories).

For the primary objective to identify and characterize metabolites in plasma, urine, and feces, the endpoint is the metabolic profile of (¹⁴C)-OPC-61815 and identification of radiolabeled metabolites present at >10% of the total drug-related exposure (AUC) plasma (calculated and reported separately in the metabolite profiling report [Covance study: 8405604] by Covance Laboratories).

3.1. Secondary Endpoints

The secondary endpoints are adverse events (AEs), clinical laboratory evaluations, physical examination findings, vital signs (blood pressure, pulse rate), body weight, and 12-lead electrocardiogram (ECG) parameters.

4. STUDY DESIGN

This will be a Phase I, single-site, open-label, nonrandomized, single IV dose trial in healthy male Japanese subjects.

Potential subjects will be screened to assess their eligibility to enter the trial within 28 days prior to the dose administration. Subjects will be enrolled and admitted into the trial site on Day -1. On Day 1, all subjects will receive a single IV infusion of 16 mg (¹⁴C)-OPC-61815, containing approximately 75.1 µCi (2.78 MBq), over 60 minutes (55 to 65 minutes, inclusive) in the fasted state.

It is planned for at least 8 subjects to be dosed to ensure that 6 subjects complete the IV infusion. Up to a maximum of 10 subjects will be dosed in total.

Subjects will be confined to the trial site until at least Day 9. Subjects will be discharged from the trial site on Day 9 if the following discharge criteria are met:

- $\geq 90\%$ mass balance recovery, and/or
- < 1% of the total radioactive dose is recovered in combined excreta (urine and feces) in 2 consecutive 24-hour periods.

If these criteria are not met by Day 9, subjects will remain at the trial site until any one of the discharge criterion are met up to a maximum of Day 10 to continue 24-hour blood, urine, and feces collections for total radioactivity, unless otherwise agreed upon by the sponsor and investigator.

[figure not shown]
If criteria are not met by Day 10, subjects may be asked to collect 24-hour excreta samples on up to 2 further occasions on a nonresidential basis to allow extrapolation of urinary and fecal excretion. If needed, the 2 additional 24-hour nonresidential collections will start on Days 10 and 11 (to be brought to the trial site at the end of the collection interval on Days 11 and 12, respectively). If on the second occasion the subject has still not met the desired criterion, then the subject will be discharged from the trial, per investigator and sponsor decision.

Final Discharge from trial will be day of discharge from residential treatment period or the day of last outpatient visit if required to attend them based on the discharge criteria. The total duration of trial participation for each subject (from Screening through Final Discharge from trial) is anticipated to be a maximum of approximately 40 days.

The start of the trial is defined as the date the first enrolled subject signs an informed consent form (ICF). The point of enrollment occurs at the time of subject number allocation. The end of trial is defined as the last date of contact or the date of final contact attempt for the last subject completing or withdrawing from the trial.

A schematic of the study design is presented in [Figure 1](#).

Figure 1: Study Design

^a Subjects can be discharged on Day 9 if the following discharge criteria are met: $\geq 90\%$ mass balance recovery and/or $< 1\%$ of the total radioactive dose is recovered in combined excreta (urine and feces) in 2 consecutive 24-hour periods. If the discharge criteria are not met, subjects will be asked to remain resident within at the trial site and additional 24-hour collection (blood, urine, and feces) for total radioactivity will continue until these criteria are met, up to a maximum of Day 10.

^b Up to 2 additional 24-hour nonresidential collections (urine and feces) for total radioactivity may occur if discharge criteria have not been met by Day 10. Subjects will collect excreta samples at home for the 24-hour period prior to the clinic visit and deliver them to the trial site at the end of the collection interval, within 24 hours.

5. SAMPLE SIZE JUSTIFICATION

No formal statistical assessment of sample size has been conducted. The sample size chosen for this trial is common in human radiolabeled studies and is considered sufficient to achieve the objectives of the trial. It is planned for at least 8 healthy male Japanese subjects to be dosed to ensure that 6 subjects complete the IV infusion. Up to a maximum of 10 subjects will be dosed in total.

6. STUDY TREATMENTS

The study treatment is (¹⁴C)-OPC-61815.

7. DEFINITIONS OF POPULATIONS

Any protocol deviations will be considered prior to database lock for their importance and taken into consideration when assigning subjects to populations.

7.1. All Subjects Population

The all subjects population will include all subjects who signed the ICF and had any study assessment recorded in the database per the protocol.

7.2. Safety Population

The safety population will include all subjects that received (¹⁴C)-OPC-61815.

7.3. Pharmacokinetic Population

The PK population will include all subjects that received (¹⁴C)-OPC-61815 (full dose within the time frame of 55 to 65 minutes, inclusive) and have evaluable PK data.

8. STATISTICAL METHODOLOGY

8.1. General

Listings will be provided for all data captured in the database, with the exception of medical history. Listings will include all subjects assigned to the all subjects population and include data up to the point of study completion or discontinuation. Any subject who discontinued the study will be identified accordingly in the listings. Summaries will include the subjects assigned to the relevant population based on data type.

Data analysis will be performed using the SAS® statistical software package Version 9.4 (or higher if upversioned during the study).

Analysis Data Model (ADaM) datasets will be prepared using Clinical Data Interchange Standards Consortium (CDISC) ADaM Version 2.1 (or higher if upversioned during the study) and CDISC ADaM Implementation Guide Version 1.1 (or higher if upversioned during the study). Pinnacle 21 Community Validator Version 2.2.0 (or higher if upversioned during the study) will be utilized to ensure compliance with CDISC standards.

Where reference is made to 'all calculations', this includes, but is not limited to, summary statistics.

8.1.1. Calculation of the Summary Statistics

For continuous data the following rules will be applied:

- Missing values will not be imputed, unless specifically stated otherwise.
- Unrounded data will be used in the calculation of summary statistics.
- If number of subjects with valid observations (n) <3, summary statistics will not be calculated, with the exception of n, minimum, and maximum.
- As Early Termination data is not associated with any scheduled timepoint, it will be excluded from all calculations of summary statistics.

For categorical data the following rules will be applied:

- If the categories of a parameter are ordered (eg, AE severity), all categories between the possible minimum and maximum categories will be included, even if $n = 0$ for a given category. If the categories are not ordered (eg, race), only those categories for which there is at least 1 subject represented will be included.
- Missing values will not be imputed, with the exception of AEs where the ‘worst-case’ approach will be taken (see [Section 8.6.1](#)), or unless specifically stated otherwise. A ‘missing’ category will be included for any parameter for which information is missing. This will ensure that the population size totals are consistent across different parameters.

8.1.2. Repeat and Unscheduled Readings

For vital signs and ECG data only, any predose value recorded in addition to the original value or a postdose value recorded within 15 minutes of the original value will be defined as a repeat value; any postdose value recorded more than 15 minutes after the original value will be defined as an unscheduled value. For all other data types (eg, laboratory parameters), any value recorded in addition to the original value will be defined as an unscheduled value.

The original value will be replaced by the last associated repeat value in all calculations.

As unscheduled values are not associated with any scheduled timepoint, they will be excluded from all calculations.

8.2. Subject Disposition and Population Assignment

Subject disposition and population assignment will be listed.

A summary table will be provided, based on the all subjects population.

8.3. Screening Demographics

The screening demographics including age, sex, race, ethnicity, country, height, body weight, and body mass index will be listed.

A summary table will be provided, based on the safety population.

8.4. Prior and Concomitant Medication

Prior medication will be defined as medication that ends prior to the start of the infusion. Concomitant medication will be defined as medication that starts after the start of the infusion or starts but does not end prior to the start of the infusion.

Prior and concomitant medications will be coded using the World Health Organization Drug Dictionary (WHODrug) Global, Format B2, Version September 2018 (or later if upversioned during the study). Prior and concomitant medications will be listed.

8.5. Pharmacokinetic Assessments

8.5.1. Pharmacokinetic Analysis

The following PK parameters will be determined where possible from the plasma concentrations of OPC-61815 free form and OPC-41061, and total radioactivity in whole blood and plasma using non compartmental methods performed using Phoenix WinNonlin (Certara USA Inc, Version 8.1 or higher):

Parameter	Definition
AUC _t	area under the concentration-time curve calculated to the last observable concentration at time t
AUC _∞	area under the concentration-time curve from time 0 to infinity
%AUC _{extrap}	percentage of AUC that is due to extrapolation from the last measurable concentration to infinity
C _{max}	maximum peak concentration
t _{max}	time to maximum peak concentration
t _{last}	time of last measurable (positive) concentration
t _{1/2,z}	terminal-phase elimination half-life
CL	total body clearance (OPC-61815 free form only)
AUC _∞ Blood /Plasma Ratio	AUC _∞ of total radioactivity in whole blood relative to AUC _∞ of total radioactivity in plasma
AUC _t Blood/Plasma Ratio	AUC _t of total radioactivity in whole blood relative to AUC _t of total radioactivity in plasma

The parameters related to the regression analysis for the terminal elimination phase shown below will be presented in the listings only and not summarized:

Regression Parameter	Definition
λ_z Lower	start of exponential fit
λ_z Upper	end of exponential fit
λ_z N	number of data points included in the log-linear regression
R ² -adj	adjusted coefficient for determination of exponential fit
λ_z	apparent terminal elimination rate constant
λ_z Span Ratio	time period over which λ_z was determined as a ratio of t _{1/2,z}

Additional PK parameters may be determined where appropriate.

The PK analysis will be carried out using actual postdose times recorded in the raw data. If actual times are missing, nominal times will be used.

Concentrations will be used as supplied by the analytical laboratory for PK analysis. The units of concentration and resulting PK parameters, with amount or concentration in the unit, will be presented as they are received from the analytical laboratory.

C_{max}, t_{max}, and t_{last} will be obtained directly from the concentration-time profiles.

When C_{max} occurs at more than 1 timepoint, t_{max} will be assigned to the first occurrence of C_{max} .

The urine and fecal PK parameters for total radioactivity in urine and feces will be calculated where possible and reported separately in the radioanalysis report by Covance Laboratories.

Identification of radiolabeled metabolites present at >10% of the total drug-related exposure (AUC) will be reported separately in the metabolite profiling report by Covance Laboratories.

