2.3 Summary of Nonclinical Pharmacokinetics

The pharmacokinetics (PK) of OPC-61815 following single IV dosing were investigated in nonfasting rats and dogs. In both species, the plasma concentrations of OPC-61815 (disodium salt [free form]) and its active metabolite OPC-41061 increased dose-dependently. The extrapolated plasma concentration at time zero (C₀) and the area under the concentration-time curve (AUC) from time zero to infinity (AUC_∞) of OPC-61815 (free form) in male rats were both 1.6 times higher than those in female rats. A sex difference in the plasma concentration-time course of OPC-41061 was observed, with the maximum peak concentration of the drug (C_{max}) and AUC_∞ in female rats being respectively 2.4 and 5.8 times higher than those in male rats, indicating a higher plasma

concentration in females. In dogs, the C_0 and AUC_{∞} of OPC-61815 (free form) in males were both 0.6 times those in females, while no clear sex difference was observed for OPC-41061. In both species, OPC-41061 was detected in plasma at 5 minutes postdose, indicating rapid hydrolysis from OPC-61815 to OPC-41061.

Following a single IV dose of (^{14}C)-OPC-61815 at 12.75 mg/kg to male rats, radioactivity was distributed into the liver, small intestine, kidney, and adrenal gland at higher levels than the plasma C_{\max} . Although, the plasma concentration of radioactivity was lower in female rats than in male rats, no sex differences were observed in the tissue concentrations of radioactivity. At 168 hours postdose, the concentrations of radioactivity were below the lower limit of quantification in almost all tissues. As a result of quantitative autoradiography in pregnant rats, radioactivity concentrations in all fetal tissues were comparable to or lower than the blood concentration in the dams, indicating low transfer of OPC-61815 to fetuses.

The distribution of radioactivity to blood cells was 1.24% to 14.69% in male rats, 1.40% to 26.04% in female rats, and 0.49% to 18.03% in male dogs, indicating low distribution to blood cells in both species.

Following a single IV dose of OPC-61815 to male rats and dogs, in rats, the AUC_{∞} of the metabolites DM-4103 and DM-4107 were respectively 1.5 to 4.0 times and 0.17 to 0.62 times that of OPC-41061, and in dogs, the plasma concentrations of DM-4103 and DM-4107 were both lower than that of OPC-41061.

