4.3 Dosing Rationale

A single dose level of 16 mg, containing approximately 75.1 μ Ci (2.78 MBq) of (^{14}C)-OPC-61815, will be administered to each subject. This equates to a radioactivity exposure of approximately 1 mSv. The radioactive dose is an acceptable dose to give to healthy subjects and is considered adequate to define the disposition of (^{14}C)-OPC-61815.

The committed effective radiation doses to be administered have been calculated by Public Health England's (PHE) Centre for Radiation, Chemical, and Environmental Hazards, based on the results of a preclinical mass balance trial and a quantitative whole body autoradiography trial.⁴ The effective radiation dose is defined as being within dose limits for members of the public (Category II trial, World Health Organization)⁵ with a minor associated risk (risk Category IIa, ICRP).³

In order to provide the optimal conditions for the objectives of the trial to be met, the radioactive dose considered for administration will be reviewed following calculation by PHE, together with any bioanalytical data from the preclinical species to ensure radioactivity concentrations in urine, feces, and plasma are detectable for sufficient periods postdose.

Intravenous administration was chosen since this is the intended clinical route of administration. Based on the nonclinical data and the known PK of OPC-61815, the sample collection timing and duration of this trial are considered adequate to achieve the trial objectives.

A 16-mg dose of (^{14}C)-OPC-61815 is within the anticipated clinical dose range and is considered to be high enough to fully characterize the single IV dose PK of the parent compound.

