8.2 Pharmacokinetic Assessments

8.2.1 Pharmacokinetic Blood/Plasma Samples

Blood samples will be collected by venipuncture or cannulation at the times indicated in the Schedule of Assessments ([Table 1.3-1](#)) for determination of OPC-61815 free form and OPC-41061 concentrations, total radioactivity, and metabolite profiling and identification. Blood samples will be collected from the contralateral arm to the arm/hand used for dose administration.

Blood samples will be collected in vacutainers containing K2EDTA and processed into plasma. Approximately 1×2 mL blood sample will be collected for total radioactivity in whole blood and approximately 1×5 mL blood sample will be collected for total radioactivity in plasma. Approximately 1×3 mL blood sample will be collected for OPC-61815 free form and OPC-41061 concentrations in plasma. Approximately 1×10 mL blood sample will be collected for metabolite profiling and identification in plasma.

Procedures for collection, processing, and shipping of blood samples will be detailed in a separate document. If any unknown metabolites are detected and further investigation is necessary, a part of the plasma samples will be shipped on dry ice to the sponsor (Otsuka Pharmaceutical Co., Ltd., Tokushima Research Institute) and used for the structure elucidation of unknown metabolites, which will be conducted separately. The investigation of these unknown metabolites will be reported separately, and the report will not be appended to the clinical study report.

The dates and times of blood collections will be documented in the subject's eCRF.

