8.5.1.1. Criteria for Handling Concentrations Below the Limit of Quantification

Predose concentration values that are below the level of quantification (BLQ) will be set to 0 and postdose concentration values that are BLQ will be set to missing for the purposes of PK analysis, with defined exceptions as follows;

- If there are late positive concentration values following 2 BLQ concentration values in the apparent terminal phase, these values will be evaluated. If these values are considered to be anomalous, they will be set to missing.
- If an entire plasma/blood concentration-time profile is BLQ, the profile will be excluded from the PK analysis.
- If a predose plasma/blood concentration is missing, this value will be set to 0 by default.

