8.5.1.2. Criteria for the Regression Analysis of the Terminal Elimination Phase

- At least 3 data points will be included in the regression analysis and preferably should not include C_{max} .
- When assessing terminal elimination phases, the adjusted coefficient of determination for exponential fit (R^2 -adj) will be used as a measure of the goodness of fit of the data points to the determined line.
- The λ_z will not be assigned if the R^2 -adj value of the regression line is <0.8. In cases where the λ_z is not assigned all regression based parameters (including R^2 -adj) will not be calculated.
- Time period used for the estimation of $t_{1/2,z}$ will be calculated over a time period of at least 2 half-lives (λ_z Span Ratio >2), where possible. Where λ_z Span Ratio <2 the robustness of $t_{1/2,z}$ will be discussed in the CSR.

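### The whole-blood/plasma AUCt ratio has no common end time, so it compares different time windows whenever the two matrices have different tlast

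*SAP*

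**What the plan says.** SAP 8.5.1 defines AUCt as the "area under the concentration-time curve calculated to the last observable concentration at time t". It reads tlast directly from each concentration-time profile. SAP 8.5.1.1 adds that "postdose concentration values that are BLQ will be set to missing for the purposes of PK analysis". The end of the AUCt interval is therefore specific to each subject and each matrix.

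The same SAP table defines the AUCt Blood/Plasma Ratio as AUCt "of total radioactivity in whole blood relative to AUC _t of total radioactivity in plasma". SAP 3.1 lists these "AUC ratios of whole blood total radioactivity relative to plasma total radioactivity" under Primary Endpoints, for both AUC∞ and AUCt. Protocol 9.4.3.2 lists the same ratios under the primary objectives.

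No rule for unequal tlast appears in Protocol 9.4.3.2, SAP 3.1, or SAP 8.5.1 to 8.5.3, which cover the BLQ, terminal-slope, AUC, anomalous-value and presentation rules.

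**The concern.** A ratio of two AUCs describes how radioactivity divides between blood and plasma only if both cover the same interval. If blood becomes unquantifiable first, the denominator keeps accumulating area after the numerator has stopped, and the ratio is too low. If plasma is lost first, it is too high. Either way, part of the result reflects the assay.

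Earlier loss in blood is plausible here, though not certain:

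- Protocol 2.3 reports nonclinical findings "indicating low distribution to blood cells in both species". Blood concentrations should then lie below plasma and reach a similar LLOQ sooner.
- Protocol 4.3 has the radioactive dose reviewed "to ensure radioactivity concentrations in urine, feces, and plasma are detectable for sufficient periods postdose". Whole blood is not named.
- Protocol 8.2.1 states that a 2 mL "blood sample will be collected for total radioactivity in whole blood", against 5 mL of blood for the plasma measurement.
- From 24 h onward the scheduled samples are 24 h apart (Protocol Table 1.3-1), so losing one more sample moves the end time by a full day.

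The two AUC ratios are the only blood/plasma comparison that either document plans. The AUC∞ ratio is not always available: under SAP 8.5.1.2, where λz "is not assigned all regression based parameters" are left uncalculated.

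**Working it through.** The plan states no value for this ratio, so there is no figure to reproduce. The calculations below show what the written rule yields under stated assumptions.

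**From the documents.** Sampling at 0, 1, 1.5, 2, 3, 4, 6, 12, 24, 48, 72, 96, 120, 144 and 168 h, with a 1 h infusion (Protocol Table 1.3-1). Extra blood draws for subjects who stay beyond Day 9 are left out. AUC by linear trapezoids (SAP 8.5.1.3). Share of radioactivity in blood cells, f, from 0.49% (male dogs) to 26.04% (female rats) (Protocol 2.3).

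**Assumed.** Haematocrit 0.45, constant blood/plasma ratio over time, and all half-lives and LLOQs.

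**Plausible true ratio.** Blood/plasma = (1 - Hct)/(1 - f). This gives 0.55/0.9951 = 0.553 and 0.55/0.7396 = 0.744, so 0.55 to 0.74 was used.

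**Bias.** (ratio with each AUC ended at its own tlast) / (ratio with both ended at the earlier tlast) - 1.

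**Worked case.** Bi-exponential decline with half-lives 4 h and 48 h, slow-phase coefficient 5% of the total, true ratio 0.65, LLOQ 2% of plasma Cmax in both matrices, plasma Cmax scaled to 1.

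- Plasma is 0.0562 at 24 h, 0.0276 at 48 h and 0.0193 at 72 h, so plasma tlast is 48 h.
- Blood is 0.0365 at 24 h and 0.0179 at 48 h, so blood tlast is 24 h.
- Plasma AUC to 24 h is 7.298. The 24 to 48 h trapezoid adds 24 × (0.0562 + 0.0276)/2 = 1.006, so plasma AUCt is about 8.303.
- Blood AUCt is 0.65 × 7.298 = 4.744.
- Ratio as the SAP defines it: 4.744/8.303 = 0.571, a bias of -12%. Common-interval ratio: 4.744/7.298 = 0.650.

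The AUC∞ ratio does not rescue this case. With terminal fits starting at 1.5 h, it is 0.582 (-10%). Both fits pass SAP 8.5.1.2: adjusted R² is 0.99 (blood) and 0.89 (plasma), and both span ratios exceed 4. Extrapolation is only 5.8% and 4.0%, so %AUCextrap raises no alarm.

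**One-compartment scenarios.** Half-life 6 to 48 h, true ratio 0.55 to 0.74; mean bias over all profiles, by plasma LLOQ as a percentage of plasma Cmax:

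| Blood LLOQ vs plasma | 0.1-0.5% | 0.5-2% | 2-5% |
|---|---|---|---|
| Equal | -0.2% | -0.7% | -2.5% |
| 1.4 times | -0.3% | -1.5% | -5.4% |
| Twice | -0.6% | -2.9% | -10.3% |

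With equal LLOQs, tlast differs in 13%, 25% and 45% of profiles, and the median bias is 0. The 1.4 factor assumes that LLOQ scales inversely with volume counted: 5 mL × 0.55 = 2.75 mL of plasma, against 2 mL of blood, gives 1.375. The AUC∞ ratio stays within 4% of the true value throughout this set.

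**Bi-exponential scenarios.** Fast half-life 2 to 6 h, slow 24 to 72 h, slow share 3 to 20%; mean bias in profiles where tlast differs:

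| Blood LLOQ vs plasma | Plasma LLOQ 1% | Plasma LLOQ 2% |
|---|---|---|
| Equal | -6% | -11% |
| 1.4 times | -9% | -16% |
| Twice | -15% | -24% |

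With equal LLOQs, tlast differs in 69% and 75% of these profiles. Averaged over all of them, the bias is -4% and -8%.

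**A wider set.** Fast half-life 3 h, slow half-life 24 to 96 h, slow share 5 to 30%, equal LLOQs of 1 to 10% of the end-of-infusion plasma level. tlast differed in 63 of 108 scenarios, with bias from -2.8% to -48.5%; it was zero in the other 45.

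**Opposite direction.** With a half-life of 24 h, a plasma LLOQ of 4% of Cmax and a blood LLOQ half of that, plasma is lost first when the true ratio is 0.65 or above, and the bias is +3.4%.

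**The case against.** The strongest reply has four parts.

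1. The documents never say that the ratio measures partition into blood cells. As a quotient of two reported exposures it is clear and reproducible, and the SAP matches the protocol. It is true that the purpose is inferred. Even so, a quotient over two different windows is hard to interpret under any reading.

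2. The calculations hold blood/plasma constant, so the common-interval ratio recovers the true value by construction. That is fair, and the calculations do not test the remedy against time-varying partition. In that situation the common-interval ratio describes only the shared interval. The mismatched ratio, however, does not describe the full profile either.

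3. Every size is assumed. No LLOQ, radioactivity half-life, haematocrit or counted volume is given; the twofold LLOQ has no documentary source, and the largest biases need LLOQs that are high relative to Cmax. This stands.

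4. A mismatch would be visible. tlast and %AUCextrap are reported for each matrix, all concentrations are listed, at most 10 subjects are dosed, and SAP 8.5.1 permits additional parameters. The separate TFL shells, not available here, might also carry flags. This lowers the consequence. Still, visibility does not correct the ratio, and permission to add a parameter is not a plan to use one.

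**Conclusion.** The concern holds. Followed exactly, the SAP produces a ratio over mismatched intervals whenever blood and plasma have different tlast, and no rule in either document prevents or corrects this.

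The bias is nil when tlast agrees, and small on average under one-compartment decline with equal LLOQs. It can exceed 10% where a slow terminal phase runs close to the LLOQ or where blood is measured less sensitively. The direction is low if blood is lost first and high if plasma is. These sizes are illustrations under assumed kinetics and LLOQs and do not predict this trial's result.

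The weight is modest. The ratio is formally among the primary endpoints, but it is descriptive and no decision rule uses it. Mass balance, excretion and metabolite identification do not depend on it. This is a cheap improvement to make before database lock.

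**What to change.** In SAP 8.5.1, define the AUCt Blood/Plasma Ratio per subject from partial AUCs, both ended at the last sampling time at which whole blood and plasma are both quantifiable. Keep each matrix's own AUCt for its own summary. Footnote the common end time for each subject and flag subjects whose tlast differs. State that the ratio describes the common interval only and is read alongside the AUC∞ ratio. As this refines the ratio in Protocol 9.4.3.2, record it in SAP Section 10.

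The cost is a sentence of definition, its footnote and one partial AUC per subject, with no new samples or assays. The drawback is that later data from the longer-lasting matrix drop out of this one ratio; they remain in that matrix's own AUCt and in AUC∞.
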